### **Concomitant Medications**

Strong to Moderate Inducers or Inhibitors of cytochrome P450 (CYP)3A, and “Sensitive” CYP3A Substrate Drugs with a narrow therapeutic index are not permitted (Appendix 7 [Section 12.7](#)).

Other “Sensitive” CYP3A drugs should be used cautiously by administering them only if the benefit/risk is favorable, using staggered administration at least 2 hours after rilzabrutinib or placebo.

Patients on proton pump inhibitor drugs should have their medication changed to histamine 2 (H2) blockers during Screening and at least 3 days before Day 1. H2 blockers should be administered at least 2 hours after rilzabrutinib or placebo.

### **Inclusion Criteria**

Patients may be included in the study if ALL of the following criteria are met:

#### **Type of participant and disease characteristics**

- I01. Male or female patients, aged 18 to 80 years old with moderate to severe, newly diagnosed or relapsing PV or PF, with a clinical presentation and histopathology consistent with PV or PF (see [Section 8.4.3](#)).
- I02. Positive circulating anti-dsg1 or 3 autoantibody titer.
- I03. At Screening, PDAI score of at least 9 points for relapsing patients (diagnosed >6 months prior to Screening) or at least 15 points for newly diagnosed patients (diagnosed ≤6 months prior to Screening).
- I04. Adequate hematologic, hepatic, and renal function (including but not limited to absolute neutrophil count  $\geq 1.5 \times 10^9/L$ , hemoglobin [Hgb] >9 g/dL, platelet count  $\geq 100 \times 10^9/L$ , aspartate aminotransferase [AST] and/or alanine aminotransferase [ALT]  $\leq 1.5 \times$  upper limit of normal [ULN], albumin  $\geq 3$  g/dL, creatinine  $\leq 1.5 \times$  ULN).

#### **Sex, contraceptive/barrier method and pregnancy testing requirements**

- I05. Female patients who are of reproductive potential must agree for the duration of the study to use an effective means of contraception (eg, hormonal contraception methods that inhibit ovulation, intrauterine device, intrauterine hormone-releasing system, bilateral tubal ligation, vasectomized partner or condoms).

For females considered not to have reproductive potential:

Any woman of age  $\geq 55$  years with amenorrhea for >1 year, will be considered as having confirmed menopause and follicle-stimulating hormone (FSH) or pregnancy testing will not be needed. Postmenopausal females <55 years of age (defined as amenorrhea >1 year) must have menopause confirmed by elevated

FSH levels at screening. Surgically sterile females do not require any further confirmation of menopause and will not be considered to have reproductive potential.

For participants in Germany, please see specific instructions in Appendix 10 [Section 12.10](#).

### **Informed Consent**

- I06. Able to provide written informed consent and agreeable to the schedule of assessments.

### **Exclusion Criteria**

Patients will be excluded from the trial if any of the following criteria are met:

#### **Medical conditions**

- E01. Suspected paraneoplastic pemphigus and other forms of pemphigus that are not pemphigus vulgaris or pemphigus foliaceus.
- E02. Previous use of a Bruton tyrosine kinase (BTK) inhibitor.
- E03. Pregnant or lactating women.
- E04. Electrocardiogram (ECG) findings of QT corrected for heart rate (QTc) >450 msec (males) or >470 msec (females), poorly controlled atrial fibrillation (ie, symptomatic patients or a ventricular rate above 100 beats/min on ECG), or other clinically significant abnormalities.
- E05. A history of malignancy of any type within 5 years before Day 1, other than surgically excised non-melanoma skin cancers or in situ cervical cancer.

#### **Prior/concomitant therapy**

- E06. Use of immunologic response modifiers as concomitant medication and with the following washout periods: A) stop **at least 2 weeks prior to Screening**: mycophenolate mofetil, azathioprine, methotrexate, cyclosporine, dapsone, intravenous immunoglobulin (IVIg), Kinaret (anakinra), Enbrel (etanercept), or any other immunosuppressant not mentioned in this exclusion criterion; B) **12 weeks prior to Screening**: Remicade (infliximab), Humira (adalimumab), Simponi (golimumab), Orencia (abatacept), Actemra (tocilizumab), Cimzia (certolizumab), Cosentyx (secukinumab), plasmapheresis; C) **6 months prior to Screening (or shorter if there is documented B cell reconstitution for anti-CD20 drugs)**: anti-CD20 drugs such as rituximab, ofatumumab, other long-acting biologics.
- E07. Use of proton pump inhibitor drugs such as omeprazole and esomeprazole within 3 days of Day 1 (it is acceptable to change patient to H2 receptor blocking drugs prior to Day 1).

- E08. Concomitant use of known strong-to-moderate inducers or inhibitors of CYP3A within 3 days or 5 half-lives (whichever is longer) of Day 1 (Appendix 7 [Section 12.7](#)).
- E09. Use of CYP3A-sensitive substrate drugs with a narrow therapeutic index within 3 days or 5 half-lives (whichever is longer) of Day 1 and for the remainder of the trial including, but not limited to alfentanil, astemizole, cisapride, cyclosporine, dihydroergotamine, ergotamine, fentanyl, pimozone, quinidine, sirolimus, tacrolimus (topical and oral), or terfenadine.
- E010. Has received any investigational drug (or is currently using an investigational device) within the 30 days before Day 1, or at least 5 times the respective elimination half-life time (whichever is longer).
- E011. History of drug abuse within the previous 12 months.
- E012. Alcoholism or excessive alcohol use, defined as regular consumption of more than approximately 3 standard drinks per day.

**Other exclusions**

- E013. Refractory nausea and vomiting, malabsorption, external biliary shunt, or significant bowel resection that would preclude adequate rilzabrutinib/placebo absorption.
  - E014. Donation of a unit or more of blood or blood products within 4 weeks prior to Day 1.
  - E015. History of solid organ transplant.
  - E016. Positive at Screening for human immunodeficiency virus (HIV), hepatitis B (surface antigen and/or core antibodies), or hepatitis C (anti-HCV antibody confirmed with Hep C RNA).
  - E017. Positive interferon-gamma release assay (IGRA) (eg, T-spot TB Test, QuantiFERON®-TB Gold, or QuantiFERON®-TB Gold Plus (QFT Plus), at Screening. Unless, the patient has latent tuberculosis (TB) and all of the following 3 conditions are true:
    - a) Chest X-ray does not show evidence suggestive of active TB disease
    - b) There are no clinical signs and symptoms of pulmonary and/or extra-pulmonary TB disease
    - c) Documented receipt of one of the following prophylactic treatment regimens:
      - i. Oral daily Isoniazid for 6 months
      - or
      - ii. Oral daily Rifampin (RIF) for 4 months
      - or
      - iii. Isoniazid and Rifapentine weekly for 3 months (3HP)
- On a case by case basis, after discussion and approval by the Sponsor, a local TB test that is negative and is considered equivalent to 1 of the above tests may be used for eligibility. For example, if a QuantiFERON®-TB Gold, or QuantiFERON-TB Gold

Plus (QFT Plus) is indeterminate for any reason and a local blood test or T-Spot TB test is negative, the patient may be enrolled using the local result upon approval of the Sponsor.

- E18. History of serious infections requiring intravenous therapy with the potential for recurrence or currently active moderate to severe infection at Screening (Grade 2 or higher).
- E19. Live vaccine within 28 days prior to Day 1 or plan to receive one during the trial.
- E20. Any other clinically significant disease, condition [including contraindication to CS and/or inability to follow CS dosing as outlined in the protocol (see [Table 1](#) for more details)], or medical history that, in the opinion of the Investigator, would interfere with patient safety, trial evaluations, and/or trial procedures. In areas endemic for Chagas disease, screening is recommended prior to enrollment.

For participants in Germany, please see specific instructions in Appendix 10 [Section 12.10](#).

## **Outcome Measures**

### **Primary Efficacy Endpoint**

- The proportion of patients who are in CR from Week 29 to Week 37 with a CS dose of  $\leq 10$  mg/day.

### **Key Secondary Efficacy Endpoints**

- Cumulative CS dose from Baseline to Week 37
- Cumulative duration of CR with a CS dose  $\leq 10$  mg/day, from Baseline to Week 37
- Time to first CR with a CS dose  $\leq 10$  mg/day, from Baseline to Week 37

### **Other Secondary Endpoints**

- The proportion of patients who are in CR from Week 29 to Week 37 with a CS dose of  $\leq 5$  mg/day
- The proportion of patients who have a PDAI score  $< 3$  from Week 29 to Week 37 with a CS dose  $\leq 10$  mg/day
- Cumulative duration of CR with a CS dose  $\leq 10$  mg/day from Baseline to Weeks 61 and 109
- Cumulative duration of CR with a CS dose = 0 mg/day from Baseline to Weeks 61 and 109
- GTI score at Week 37
- Change in PDAI score from Baseline to Weeks 5, 13, 25, 37, 61, and 109
- Change in Autoimmune Bullous Disease Quality of Life (ABQOL) score from Baseline to Weeks 5, 13, 25, 37, 61, and 109
- Proportion of patients with ABQOL Score of zero at Weeks 5, 13, 25, 37, 61, and 109

- Change in EuroQOL-5 Dimension 5 Level (EQ-5D-5L) results (visual analog scale [VAS] results and individual dimension) scores from Baseline to Weeks 5, 13, 25, 37, 61, and 109
- Time to first CR with a CS dose  $\leq$ 10 mg/day, from Baseline to Weeks 61 and 109
- Total number of disease relapses/flares from initial CDA to Week 37
- Time to initial relapse/flare from initial CDA to Week 37
- Proportion of patients with 3 or more new lesions within 1 month that do not heal spontaneously within 1 week, or with extension of established lesions, from Baseline to Week 37
- Proportion of patients with at least one disease relapse/flare from initial control of disease activity (CDA) to Week 37
- Cumulative duration of CR with a CS dose  $\leq$ 10 mg/day, from Week 37 to Week 61
- Cumulative duration of CR with a CS dose = 0 mg/day, from Week 37 to Week 61

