### 2.2 BACKGROUND

#### 2.2.1 Overview of pemphigus

Pemphigus is a group of rare autoimmune diseases that causes painful blistering of the skin and mucous membranes (mouth, nose, throat, eyes, and genitals). Pemphigus is associated with autoantibodies to the epithelial protein, desmoglein, in about 90% of cases. Pemphigus vulgaris (PV) and pemphigus foliaceus (PF) are the main subtypes of pemphigus with PV being the most common in most parts of the world (5, 6). Pemphigus can occur at any age, but often strikes people in middle or older age. Studies have shown that some populations may be at greater risk for certain types of pemphigus. For instance, people of Jewish descent and those from India, Southeast Europe, and the Middle East are at greater risk for PV, while PF is common in South America.

PV typically begins with blisters (bullae) in the mouth, which are often mistaken for aphthous ulcers. The blisters are flaccid and are easily broken, leading to often-painful lesions or erosions. Blistering can also affect the esophagus, rectum, nose, or the lining of the eyelids. Skin lesions appear several weeks or months after the onset of mucosal erosions. PV is associated with circulating antibodies to desmoglein 3 in most cases.

PF affects the skin only, without mucosal involvement. Antibodies to desmoglein 1 are commonly detected. The natural history is chronic, and treatment is identical to that for PV.

In both types of pemphigus, Nikolsky's sign (shear force displacement of skin) can appear on perilesional skin or, in some cases, even on healthy skin. The diagnosis can be confirmed by

standard histopathological analysis and direct immunofluorescence test on affected skin. The presence of elevated anti-desmoglein antibodies is confirmatory.

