#### Type of participant and disease characteristics

- I 01. Male or female patients, aged 18 to 80 years old with moderate to severe, newly diagnosed or relapsing PV or PF, with a clinical presentation and histopathology consistent with PV or PF (see [Section 8.4.3](#)).
- I 02. Positive circulating anti-dsg1 or 3 autoantibody titer.
- I 03. At Screening, PDAI score of at least 9 points for relapsing patients (diagnosed >6 months prior to Screening) or at least 15 points for newly diagnosed patients (diagnosed ≤6 months prior to Screening).
- I 04. Adequate hematologic, hepatic, and renal function (including but not limited to absolute neutrophil count  $\geq 1.5 \times 10^9/L$ , hemoglobin [Hgb] >9 g/dL, platelet count  $\geq 100 \times 10^9/L$ , aspartate aminotransferase [AST] and/or alanine aminotransferase [ALT]  $\leq 1.5 \times$  upper limit of normal [ULN], albumin  $\geq 3$  g/dL, creatinine  $\leq 1.5 \times$  ULN).

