#### 6.1.10. GTI Scores

The Glucocorticoid Toxicity Index is a proprietary licensed instrument from Massachusetts General Hospital (Miloslavsky 2017). It was developed to assess glucocorticoid (GC)-related morbidity and GC-sparing ability of other therapies.

The GTI is composed of two components, the Composite GTI and the Specific List. The Composite GTI consists of nine domains (body mass index (BMI), glucose tolerance, blood pressure, lipid, bone mineral density, glucocorticoid-induced myopathy, skin toxicity, Neuropsychiatric toxicity, and infection) on common steroid-related adverse events anticipated to occur in  $\geq 5\%$  of patients treated in a clinical trial involving glucocorticoids. Note that for this study bone mineral density was not collected, and therefore not included in the derivation. The Specific List consists of 23 items (11 domains) that are mainly less common but serious adverse effects, serving as a complementary tool to the Composite GTI to ensure that all important elements of glucocorticoid toxicity were captured.

The domains of the Composite GTI and the specific list of the GTI will be assessed at Day 1, Week 13, Week 25, Week 37. The details on the derivations of baseline glucocorticoid toxicity score are provided in Appendix 2.

**Domain-specific score** for each patient at a visit is defined as the weight assigned based on the change in severity level as described for each domain in Appendix 3.

**Composite GTI score** for each patient at a visit is the sum of 8 domain-specific scores at each visit.

**Cumulative GTI score** is the sum of composite GTI score across visits. Two cumulative GTI scores, CWS and AIS, will be defined.

- **Cumulative worsening score (CWS)**

CWS is designed to assess cumulative GC toxicity, regardless of whether the toxicity has lasting effects or is transient. New toxicities that occur are added, but toxicities that

appear to resolve on follow-up are not removed. Thus, the CWS serves as a lasting record of GC toxicity observed and can only increase or remain the same over time.

CWS will be lower in the treatment arm compared to the placebo arm at the end of trial, if the treatment is effective at decreasing GC toxicity over time.

- **Aggregate improvement score (AIS)**

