Patients are anticipated to have some GC toxicity at baseline, the AIS would be important in establishing that the new therapy is effective at diminishing any baseline GC toxicity over time. With the AIS, toxicities can be removed if improvement occurs, and added if worsening occurs.

AIS decrease over time means that the treatment is effective in decreasing GC toxicity level, compared to placebo which may show fluctuation of CIS over time. Negative score reflects that toxicities present at baseline (or occurring during the trial) resolved over the treatment period.

The steps to calculate the CWS and AIS at Weeks 25 and 37 are described below.

**Step 1:** Calculate domain-specific worsening score (for computing CWS in Step 2) and improvement score (for computing AIS in Step 2) at each visit.

For Domains without sub-items (Body Weight, Glucose Metabolism, Blood Pressure, Lipid Metabolism, Steroid Myopathy),

- a) For worsening score, only consider positive domain-specific score at each visit. For domain with a negative domain-specific score, the worsening score will be 0.
- b) For improvement score, all domain-specific scores (could be positive or negative) at each visit will be considered.

The Skin and Neuropsychiatric domains both have sub-items. For the Skin domain, these are Acneiform Rash, Easy Bruising, Hirsutism, Atrophy/Striae, and Erosions/tears/ulcerations. For the Neuropsychiatric domain, these are Insomnia, Depression, Mania, and Cognitive Impairment.

- a) For worsening score, only the item with the highest weight is scored for any GTI interval (typically three months) with the CWS. As an example, if neither insomnia nor depression were present at the baseline visit but there is now mild Insomnia and moderate depression present at follow-up, then only the moderate depression is scored (+63 points).
- b) For improvement score, improvement as well as worsening can be recorded. Because it is conceivable that one item might improve while another worsens, the item of greatest improvement (highest absolute weight) and the item of greatest worsening (highest weight) are recorded for given GTI interval.

For Infection Domain, the worsening score and improvement score handle the scoring of infections differently, because the CWS and AIS reflect reciprocal measures of GC toxicity.

- a) For worsening score, the most severe infection in every GTI interval is scored.

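### The GTI skin domain scores erosions, and the available text has no rule keeping pemphigus lesions out of it, so the Week 37 AIS and CWS could partly reflect disease control.

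*Protocol*

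**What the plan says.** The Protocol (Synopsis and Section 3) lists "GTI score at Week 37" among the other secondary endpoints. One efficacy objective is to show less corticosteroid (CS) exposure and fewer adverse effects of CS. SAP 6.1.10 says of the GTI: "It was developed to assess glucocorticoid (GC)-related morbidity and GC-sparing ability of other therapies".

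The rest of SAP 6.1.10 sets the scoring:

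- The composite sums eight domain scores. Bone mineral density is left out because it was not collected. Assessments are on Day 1 and at Weeks 13, 25 and 37.
- A domain score is a weight determined by the change in severity level.
- The skin domain has five sub-items: "Acneiform Rash, Easy Bruising, Hirsutism, Atrophy/Striae, and Erosions/tears/ulcerations".
- For the CWS, only the highest-weighted worsening sub-item counts in an interval, and points once added are never taken away.
- For the AIS, "the item of greatest improvement (highest absolute weight) and the item of greatest worsening (highest weight) are recorded", so improvement subtracts points.
- Both cumulative scores at Week 37 are sums over Weeks 13, 25 and 37.
- The SAP reads a falling AIS, and a lower CWS on active treatment, as less steroid toxicity.

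SAP 8.3 compares Week 37 CWS and AIS between arms by ANCOVA with treatment, disease history, baseline GTI score and baseline CS dose. Baseline scoring is referred to Appendix 2, and weights and detailed derivation to Appendix 3. Neither appendix is in the text available for this review.

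On the disease, Protocol 2.2.1 says of PV: "The blisters are flaccid and are easily broken, leading to often-painful lesions or erosions". It adds that PF affects the skin only.

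**The concern.** The same physical finding, a skin erosion, can be a steroid effect or the disease itself. The visible scoring rule asks how severity has changed and not why. The protocol does make this separation for adverse events: Section 8.6.3.2 keeps expected variation in pemphigus activity out of AE reporting. No matching instruction for the GTI appears in the text available.

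The trial is designed to detect a difference between arms in lesion clearance. If pemphigus erosions are entered under this sub-item, a treatment that clears lesions could move the toxicity score with no difference in steroid harm. The GTI result could then no longer be taken, on its own, as evidence of a steroid-sparing benefit. The baseline covariates do not solve this, because the healing in question happens after baseline and may differ by arm.

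**Working it through.** The plan states no figure on this point, so there is nothing to reproduce. The check applies the SAP 6.1.10 rules to the erosion sub-item alone, with weight w. The documents do not give w.

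**Per-patient effect, in units of w.** The available text can be read as scoring change over each interval or change against baseline, because it refers to GTI intervals but its worked example compares follow-up with the baseline visit. Changes are listed for Weeks 13, 25 and 37. The CWS sums only the positive changes; the AIS sums all of them.

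| Course of the erosion | Changes | CWS | AIS |
|---|---|---|---|
| Present at baseline, healed by Week 13, scored per interval | −1, 0, 0 | 0 | −1w |
| The same, scored against baseline | −1, −1, −1 | 0 | −3w |
| No change | 0, 0, 0 | 0 | 0 |
| New in a flare at Week 25, healed by Week 37, per interval | 0, +1, −1 | +1w | 0 |

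Two things follow. Healing of baseline erosions acts on the AIS only. The CWS is reached only through new or worsening erosions, so any shift there favours the arm that has fewer of them.

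**Between-arm illustration for the AIS.** Let d be the difference between arms in the proportion of patients whose scored baseline erosions heal, and k the number of visits at which healing is counted (1 or 3). Then

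shift in mean AIS = −k × w × d.

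Both w and d are assumptions: w from 10 to 60 points and d from 0.10 to 0.35. The only sub-item weight printed in the SAP is +63, for moderate depression in another domain, so it does not fix w.

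- Counted once: −(10 × 0.10) = −1 to −(60 × 0.35) = −21 points.
- Counted at three visits: −(3 × 10 × 0.10) = −3 to −(3 × 60 × 0.35) = −63 points.
- CWS shift from healing of baseline erosions: 0 throughout.

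For any given w and d these are upper bounds. They require that pemphigus erosions are scored at all, and that the erosion item is the highest-weighted improving skin sub-item in every patient counted in d. They show the mechanism and do not estimate its size.

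**The case against.** The strongest reply is that the deciding text is missing. The GTI is a licensed instrument, its item definitions are not reproduced, and Appendices 2 and 3 could hold an attribution rule. Their absence from the text reviewed is not evidence that the plan lacks one. The visible wording also describes the domain as skin toxicity and the items as steroid-related events, so raters may never have entered pemphigus lesions. This stands, and it makes the point conditional.

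Second, entry criteria do not establish baseline skin erosions. The criterion reads "At Screening, PDAI score of at least 9 points for relapsing patients" (and at least 15 for newly diagnosed patients), but Protocol 8.4.9 allows up to 120 of the 250 PDAI points for mucosal activity, so a PV patient can qualify on mucosal disease alone. The GTI baseline is Day 1, after up to four weeks of Screening on mandated CS. This also stands and reduces the number of patients exposed to the problem.

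Third, the consequences are contained. SAP 6.1.4 treats endpoints outside the hierarchy as exploratory. Steroid sparing is tested directly by cumulative CS dose, the first key secondary endpoint, and CS-related TEAEs are tabulated (SAP 9.1.1). SAP 6.1.5.2 drops GTI data from the first rituximab dose onward, which removes later data from some severe flares. Domain-specific scores are summarised by arm and visit, so a result driven by skin would show. That summary stops at the domain, however, and cannot separate erosions from the other four sub-items.

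**Conclusion.** The concern holds in conditional form. If pemphigus skin erosions are scored, the Week 37 AIS can fall through healing of the disease and the CWS can rise through flares, so a GTI difference could partly reflect disease control. The direction favours the arm with better disease control. The size cannot be determined from the documents. It is limited to one of five sub-items in one of eight domains, and to patients in whom that sub-item is the top-weighted change. Primary and key secondary conclusions are untouched.

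Three stronger readings are tempting and are not supported:

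- A reader might infer that a drug which only heals lesions would improve both scores. The SAP's own rule gives healing of baseline erosions no effect on the CWS.
- A reader might infer that healing is in fact being counted as lower toxicity. The documents show that the scoring could allow this, not that raters do it or that no attribution rule exists.
- A reader might take the point ranges in the working as the expected bias. They rest on assumed weights and healing differences, and are upper bounds for those assumptions.

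**What to change.** In SAP 6.1.10 and 8.3, keep the full eight-domain score as the main GTI analysis. Before unblinding, prespecify a supportive ANCOVA of Week 37 CWS and AIS, each derived without the erosions/tears/ulcerations sub-item and otherwise using the same model. State that a GTI difference will be interpreted as reduced steroid toxicity only if it also holds in that analysis.

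Do not change rater instructions mid-trial. The scores are based on change, so a lesion scored at one visit and left unscored at the next under a new instruction would look like improvement.

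The cost is one extra derivation. Step 1 of SAP 6.1.10 already works at sub-item level, so no new data should be needed. The downside is that the supportive score is not the unmodified licensed instrument, which is why it should stay supportive.
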